2.4.2 Secondary Efficacy Endpoint

Safety - PREHAB program safety will be evaluated by monitoring unanticipated problems involving risk to subjects or others (UPIRSO). At each PREHAB session, the post intervention evaluation and the 3 month follow up visit the exercise physiologist or personal trainer will record any side effects or symptoms reported by the subject. Within a week the treating physician or Principal Investigator (PI) will review and classify all events. Any events meeting the definition of a UPIRSO will be documented on the UPIRSO log and/or to the IRB by the coordinator within 10 business days.

2.4.3 Exploratory Endpoints

2.4.3.1 Impact on sarcopenia we will be measured using changes in hand grip strength and the short physical performance battery measured at Baseline, Post-Intervention Evaluation and 3-month Follow Up. Changes in Muscle Mass measured at Baseline and 3-month Follow Up will also be utilized.

2.4.3.2 Health-related quality of life will be measured by changes in the PROMIS-29 and PROMIS Cancer Function 3D Profile¹⁶ scores measured at Baseline, Post-Intervention Evaluation and 3-month Follow Up.

2.4.3.3 Functional Performance will be measured by changes in the 6-minute walk test and physical performance metrics scores measured at Baseline, Post-Intervention Evaluation and 3-month Follow Up.

2.4.3.4 Hospitalizations and length of stay will be recorded from medical record review and a telephone follow-up with the patient and their caregivers at the 3-month follow up. Only hospitalizations post Baseline will be recorded.

2.4.3.5 Post-operative outcomes will be recorded from medical record review and a telephone follow-up with the patient and their caregivers at the 3-month follow up. Only operations post Baseline will be recorded. Post-operative complications will be assessed by the investigator retrospectively using the Clavien-Dindo classification system^{17,18}.

2.4.3.6 Physical Activity and Sleep will be measured by continuous activity and sleep monitoring by the Fitbit wrist worn device. The Fitbit will be worn from Baseline through to the 3-month Follow Up.

2.4.3.7 Impact of the online Pain guide will be measured by the Patient Global Impression questionnaire administered at the Post Intervention Evaluation Visit.

2.4.3.8 Impact on weight and BMI will be measured using changes in weight and BMI measured at Baseline, Post-Intervention Evaluation and 3-month Follow Up.

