2.3 Exploratory Objectives

2.3.1 To assess the impact of a PREHAB program on sarcopenia

2.3.2 To assess the impact of a PREHAB program on health-related quality of life including domains of physical function, fatigue, and social participation

2.3.3 To assess the impact of a PREHAB program on functional performance including strength and endurance

2.3.4 To assess the association between a PREHAB program and healthcare utilization including number of hospitalizations and length of stay

2.3.5 To assess the impact of a PREHAB program on post-operative outcomes including length of stay and complication rates

2.3.6 To assess the impact of a PREHAB program on continuous activity and sleep patterns

2.3.7 To assess the impact of a validated, web-based, health self-management guide designed for individuals with chronic illnesses (www.painguide.com)

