5.1.3 Self- Management

Participants will be provided with a wrist worn Fitbit device to wear continuously from the Baseline visit through to the 3 Month Follow Up Visit. The Fitbit will monitor daily physical activity, sleep, and heart rate.

Patients will be instructed to accumulate a total of 150 minutes per week of moderate aerobic training at home outside of the set sessions. This will be measured by Fitbit data. It is not a deviation if they do not complete this many minutes per week.

All patients will be given the option to access an online pain management portal. This website (www.painguide.com) from the University of Michigan provides information on the management and monitoring of symptoms and behaviors including sleep and physical activity. Participants will be provided training on how to use and interact with this online portal. Use of this platform is optional; however, participants will be encouraged to engage with the portal at least once weekly. Portal use will be assessed via self-report every two weeks.

Following completion of the 6-week intervention, patients will be given resistance bands to continue with resistance training at home. At home exercise following

the 6-week intervention is at the participants own discretion and will be monitored by Fitbit data.

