6.1.7 Physical Activity assessment

Ambulatory status, ability to complete functional assessments including 6-minute walk test, hand grip strength, short performance physical battery and performance metrics.

6.1.8 Review subject eligibility criteria**6.2 Baseline Procedures (within 14 days of first PREHAB session)**

All baseline procedures will occur after the patient is deemed to be eligible by review of the eligibility criteria.

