6.2.5 Fitbit Training and Use

- Training will include how to wear, charge and sync Fitbit
- Participants will start wearing the Fitbit continuously from the Baseline session
- Subjects who are unable to meet eligibility criteria 4.1.9 or who do meet exclusion criteria 4.2.3 will be exempt from this study task.

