6.3 Study Procedures**6.3.1 Week 1 – Week 6* (Within 14 days of Baseline)**

- 3 x weekly 1 hour PREHAB session
- Continuous activity monitoring (Fitbit)
- Unanticipated Problem review
- Optional use of the Online Pain Portal. Self-Report portal interaction.
- SOC Lab review – **If labs do not meet criteria in Section 6.2.4, STOP and call the PI**
- 150 minutes of self-managed exercise per week at home (measured by Fitbit data)

*Up to 3 missed sessions will be made up in a 7th week

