6.3.2 Post-Intervention Evaluation (Within 14 days following the last PREHAB session)

Can be on the same day as the last PREHAB session

- Vitals (Weight, BMI)
- Six-minute walk test
- Hand grip strength
- Physical performance metrics
- Short performance physical battery
- Unanticipated Problem review
- PROMIS-29 (for non-English speaking patients, an interpreter will be used for the questionnaire)
- PROMIS Cancer 3D Function Profile (for non-English speaking patients, an interpreter will be used for the questionnaire)
- Patient Global Impression of Change (Only those participants who used the Online Pain portal)
- Continuous activity monitoring (Fitbit)

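### Fitbit wear starts at a Baseline visit with no minimum lead time before session 1, so a pre-program activity and sleep level is neither guaranteed nor defined (minor)

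*Combined protocol and SAP*

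**What the plan says.** Section 2.3.6 sets the objective: "To assess the impact of a PREHAB program on continuous activity and sleep patterns". Section 2.4.3.6 gives the endpoint as continuous monitoring with a wrist device: "The Fitbit will be worn from Baseline through to the 3-month Follow Up". Section 6.2.5 agrees: "Participants will start wearing the Fitbit continuously from the Baseline session".

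The timing of that visit appears in the heading of section 6.2, "Baseline Procedures (within 14 days of first PREHAB session", and in the heading of section 6.3.1, "Week 1 – Week 6* (Within 14 days of Baseline". The Time and Events table repeats the limit. All three give a maximum and none gives a minimum.

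Other exploratory endpoints are written as changes across visits. Section 2.4.3.3, for example, reads "Functional Performance will be measured by changes in the 6-minute walk test and physical performance metrics scores" and names Baseline as the first measurement. Sections 2.4.3.1, 2.4.3.2 and 2.4.3.8 follow the same pattern; section 2.4.3.6 does not. Section 8.3 describes analyses for the primary and secondary endpoints and does not mention the exploratory ones.

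**The concern.** A walk test, a grip test or a questionnaire yields its pre-program value at the Baseline visit itself. A wearable yields one only if days of recording accumulate between that visit and session 1. Baseline therefore secures a reference for the other change endpoints but not for this one.

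The reference matters because the study is single arm, so the participant's own earlier level is the only available comparison. The program also writes activity directly into the record. Section 3.0 prescribes three supervised one-hour sessions a week, and section 5.1.3 adds home exercise: "Patients will be instructed to accumulate a total of 150 minutes per week of moderate aerobic training at home". Together that is 3 × 60 + 150 = 330 minutes a week if fully followed. Without a pre-program level, one cannot say whether this activity adds to a participant's usual activity or replaces it.

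At stake is one exploratory objective. The loss is permanent, because no analysis can restore days that were never recorded.

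**Working it through.** **The plan's own figures.** The documents state no figure for the Fitbit endpoint. The one statistical figure that can be reproduced concerns the primary test: P(X ≥ 10 | n = 16, p = 0.50) = 0.2272, which agrees with the 22.7% in section 8.1. It does not depend on Fitbit timing and would not change.

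**Inputs.**
- Start of wear: the Baseline session (sections 2.4.3.6, 5.1.3, 6.2.5).
- Gap g from the Baseline date to the session 1 date: 0 to 14 days (sections 6.2, 6.3.1, Time and Events table).
- Benchmark for a usable reference: 7 full days, so that each day of the week is covered once. This is an assumption; the documents set no benchmark.

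**Full recording days before session 1.** Neither the Baseline day nor the session 1 day is a full pre-program day, so d = max(0, g − 1).

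| Gap g (days) | Full pre-program days d |
|---|---|
| 0 | 0 |
| 1 | 0 |
| 4 | 3 |
| 7 | 6 |
| 8 | 7 |
| 14 | 13 |

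Of the 15 permitted gaps, only g = 8 to 14 (7 values) give d ≥ 7. This counts what the window allows. It does not predict how many participants fall in each row, since the documents give no distribution of gaps.

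**Uneven precision.** Suppose, for illustration, that days within a person are independent with equal standard deviation σ. The error of the reference mean is then σ/√d. A participant with d = 3 has a reference error √(13/3) = 2.08 times that of a participant with d = 13. With d = 0 there is no reference at all.

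**Does another passage fill the gap?** No. Section 2.4.3.6 gives no reference window, valid-day rule, summary measure or change score, and section 8.3 adds nothing for exploratory endpoints.

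**The case against.** The strongest reply is that the 14-day window already allows a usable pre-program period, so anyone with a reasonable gap can have a before/during/after comparison. That is right. A reader might infer that the objective cannot be estimated at all, but the documents do not support that reading. They show only that a reference is not assured.

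Second, starting the program on the day of Baseline is allowed only by silence. The one explicit same-day permission, "Can be on the same day as the last PREHAB session", is in section 6.3.2 and concerns the post-intervention visit. Baseline also carries a full test battery, questionnaires and device training. Nothing shows that a same-day start is planned or common, so the number of participants affected is unknown. This stands as a limit on size, but it does not supply a minimum gap.

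Third, a run-in would not produce a causal effect. There is no control group, section 6.2.4 expects concurrent neoadjuvant therapy, and section 5.1.3 lists the Fitbit among the program's own components, so even wear before session 1 is not free of intervention. This stands, and it is why the contrast should be labelled descriptive.

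Fourth, section 5.1.3 gives the Fitbit uses that need no earlier period: measuring home minutes during the program and following home exercise afterwards. True, but those uses do not answer objective 2.3.6.

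**Conclusion.** The point holds in a limited form. Following the plan as written, a participant may enter session 1 with anywhere from 0 to about 13 full days of prior recording, and no rule says which days form the reference. Change in activity and sleep may be inestimable for some of the 16 participants and unevenly precise for others. Participants exempt from the Fitbit under sections 4.1 and 4.2, and those who miss the 3-month visit that section 5.6 requires for exploratory evaluability, would reduce the usable number further.

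This rests on reading the absence of a minimum gap as permission for short gaps, and on the assumed 7-day benchmark for the count of adequate gaps.

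Two further inferences should be resisted. Pre-program days as a share of total wear time do not measure estimability: seven reference days carry the same information however long follow-up lasts. Repeating the Godin-Shephard questionnaire is not a clean substitute either. Entry requires a score of 23 or less, so using that screening score as the starting value invites regression to the mean.

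The point is minor: the endpoint is exploratory, and the primary, the safety endpoint and the sample size are unaffected.

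**What to change.** 1. In section 6.2.5 and the Time and Events table, either issue the Fitbit once eligibility is confirmed, or schedule Baseline so that about 7 full wear days precede session 1. By the count above, the second option means a gap of 8 to 14 days, which fits the existing window. State the minimum number of wear days under either option, because the documents set no minimum interval between confirmed eligibility and Baseline.
2. In section 2.4.3.6, define the endpoint as change from the mean over the days before session 1 to (a) the mean over the program period, including the optional 7th week where used, and (b) the mean over follow-up. Name the activity and sleep summaries and a valid-day rule, and say how participants without enough reference days will be shown.
3. State that the result is a descriptive before/during/after change, not a causal effect, and align the wording of section 2.3.6.

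The cost is a short amendment plus either a slightly earlier device hand-out or a few days' spacing between Baseline and session 1 for some participants. No new visit or instrument is needed.

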3.0 STUDY DESIGN

This is single site, pilot study designed to test the feasibility of a 6-week PREHAB program in pancreatic patients. All patients will participate in a 6-week supervised PREHAB program with either an exercise physiologist or personal trainer. Each week, patients will undergo 3 x 1 hour supervised training sessions consisting of moderate intensity aerobic training and resistance training. In addition to the supervised sessions,

patients will be instructed to accumulate a total of 150 minutes per week of moderate aerobic training at home.

This study has been designed to assess the hypothesis that a supervised PREHAB program is feasible in pancreatic cancer patients.

3.1 Inclusion of Women and Underrepresented Minorities

The total number of subjects involved in the study will be 16. Of those, we estimate that approximately 20% will be cisgender women. The estimated racial/ethnic breakdown of the study may approximately be that 15% may be Black or African American, 5% may be Asian, and 1% may be Native Hawaiian-Pacific Islander. Approximately 15% of the subjects may be Hispanic. While this provides only an estimated breakdown of the study population, efforts should be made to ensure equitable recruitment of individuals that meet the above eligibility requirements.

4.0 PATIENT ELIGIBILITY

4.1 Inclusion Criteria

- 4.1.1** Pancreatic cancer diagnosis (any stage)
- 4.1.2** Age \geq 18 years
- 4.1.3** Independent ambulation and activities of daily living (Discretion of referring/treating oncologist)
- 4.1.4** Godin-Shephard Leisure-Time Physical Activity Questionnaire score of \leq 23
- 4.1.5** Physically able to complete functional assessments including 6-minute walk test, hand grip strength, short performance physical battery and performance metrics
- 4.1.6** Answers no to all questions on PAR-Q **OR** is cleared to participate by their treating oncologist
- 4.1.7** Written informed consent obtained from subject and ability for subjects to comply with the requirements of the study

Inclusion criteria for remote monitoring of physical activity (Fitbit) and online Pain portal only (failure to meet inclusion criterion 4.1.9 should not preclude subjects from participating in main study):

- 4.1.8** Access to a smart device capable of Fitbit syncing and accessing the online Pain portal (www.painguide.com)

4.2 Exclusion Criteria

- 4.2.1** Current pregnancy

Exclusion criteria for remote monitoring component of the study with Fitbit only (failure to meet exclusion criterion 4.2.3 should not preclude the subject from participating in main study):

- 4.2.2** Using a pacemaker, implantable cardiac defibrillator, neurostimulator, cochlear implants (removable hearing aids permitted), or other electronic medical equipment, unless the treating physician deems study participation safe.

5.0 INTERVENTION PLAN

This is a multimodal PREHAB program with the following elements:

5.1 PREHAB Components

5.1.1 Functional Exercise

Participants will attend 3 x weekly 1hr in-person supervised exercise sessions with a trained exercise physiologist or personal trainer for a 6-week period. Sessions will be scheduled around the participants and the trainer's availability. Sessions will be held in the hospital gym at Cedars-Sinai – [name]. During these sessions patients will undergo aerobic and resistance training.

Missed Sessions: Patients will be strongly advised not to miss any sessions. Sessions missed due to cancellations from the study team or participant (due to sickness, holidays, etc.) will be made during an optional 7th week following the 6-week intervention. There will be up to three make-up sessions. Patients will not be required to attend these make-up sessions but if they do not attend it will count as a missed session.

5.1.2 Nutrition

If patients have not previously been referred to a hospital dietitian during their pancreatic cancer care, they will receive a referral prior to their first PREHAB session.

5.1.3 Self- Management

Participants will be provided with a wrist worn Fitbit device to wear continuously from the Baseline visit through to the 3 Month Follow Up Visit. The Fitbit will monitor daily physical activity, sleep, and heart rate.

Patients will be instructed to accumulate a total of 150 minutes per week of moderate aerobic training at home outside of the set sessions. This will be measured by Fitbit data. It is not a deviation if they do not complete this many minutes per week.

All patients will be given the option to access an online pain management portal. This website (www.painguide.com) from the University of Michigan provides information on the management and monitoring of symptoms and behaviors including sleep and physical activity. Participants will be provided training on how to use and interact with this online portal. Use of this platform is optional; however, participants will be encouraged to engage with the portal at least once weekly. Portal use will be assessed via self-report every two weeks.

Following completion of the 6-week intervention, patients will be given resistance bands to continue with resistance training at home. At home exercise following

the 6-week intervention is at the participants own discretion and will be monitored by Fitbit data.

5.1.4 Muscle Mass calculation

The SOC Abdomen CT scans will be reviewed for muscle mass. CT images will be analyzed via Analyze 14.0 software by the Cedars-Sinai Imaging Core or trained personal.

5.2 PREHAB intensity / injury

Patients will participate in specific PREHAB exercises as they are able. Aerobic activity will be adjusted per participant to a level of 4-6 on a modified Borg Scale. Level of resistance for each exercise will be adjusted by the exercise trainer/physiologist such that repetitions are being performed at ~75% of the one repetition maximum. Chest specific exercises including chest press, dips, and push-ups will be omitted for patients with ports. Any patients experiencing symptoms of dizziness, lightheadedness or dyspnea will be instructed to take a break until symptoms resolve. Patients with unresolving symptoms or more serious symptoms like chest pain will be referred to the cancer rehabilitation physician who will evaluate the patient and refer to acute services as indicated.

Patients who sustain injuries related to the PREHAB sessions may remain on the study as long as their injury does not prevent them from completing the exercise protocol.

5.3 Standard of Care (SOC) Procedures

As SOC, patients will undergo Computed Tomography (CT) scans periodically throughout their pancreatic cancer diagnosis and treatment. This study will review SOC Abdomen CT scans undertaken closest to both the Baseline and 3 month follow up visit.

Patients will also undergo SOC labs periodically throughout their pancreatic cancer diagnosis and treatment. This study will review SOC labs undertaken closest to each PREHAB session to determine safe physical activity participation.

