5.4 Duration of Study Participation

The study duration per subject will be approximately 23 weeks, with up to 4 weeks of screening, up to 7 weeks on treatment, and 3 months of follow-up.

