6.2.3 SOC Abdomen CT scan

- Document date of closest SOC Abdomen CT scan (ok if occurred prior to consent or greater than 14 days prior to first PREHAB session)

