6.4.3 SOC Abdomen CT scan

- Document date of closest SOC Abdomen CT scan (ok if occurs outside of the 3 month \pm 14 days window)

6.4.4 Healthcare Utilization Assessment (May be assessed by chart review, in-person discussion at visit and/or phone call)

- Number of hospitalizations
- Reason for hospitalization
- Days hospitalized
- Disposition: continued therapy, hospice, death, other
- If underwent resection then evaluate post-op complications - Post-operative complications will be assessed using the Clavien-Dindo classification system^{17,18}

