6.5 Time and Events Table

	Screening (Within 28 days of Baseline)	Baseline (Within 14 days of first PREHAB session)	Week 1 – Week 6¹	Post-Intervention Evaluation (Within 14 days of last PREHAB session)	3 Month Follow-Up (± 14 days)
Informed Consent	X				
Confirm Eligibility	X				
Medical History	X				
Demographics	X				
Pregnancy status ²	X				
Godin Leisure-Time Exercise Questionnaire	X				
PAR-Q	X				
Physical Activity Assessment	X				
Vitals (Height, Weight, BMI) ³		X		X	X
Six Minute Walk Test		X		X	X
Hand Grip Strength		X		X	X
Physical Performance Metrics		X		X	X
Short Performance Physical Battery		X		X	X
Unanticipated Problem review			X	X	X
PROMIS-29		X		X	X
PROMIS Cancer 3D Function Profile		X		X	X
SOC Abdomen CT Scan ⁴		X			X
SOC Lab Test Review		X	X ⁵		
Fitbit activity monitoring ⁶		X	X	X	X
Dietitian referral ⁷		X			
Online Pain platform ⁸ Training		X			
Online Pain platform use ⁸			X		
Online Pain platform compliance			X ⁹		
3 x Weekly 1HR PREHAB session			X		
Patient Global Impression of Change ¹⁰				X	
Healthcare Utilization Assessment					X

BMI: Body Mass Index, CT: Computed Tomography, PAR-Q: Physical Activity Readiness Questionnaire

1. Up to 3 missed sessions will be made up in a 7th week
2. Pregnancy status confirmed with patient and via medical record review

3. Height will only be collected at Baseline
4. CT scans completed closest to baseline and 3-month follow-up will be used, even if they occurred outside of the relevant visit window.
5. SOC labs will be reviewed prior to each PREHAB session
6. Fitbit use is only required by those who met eligibility criteria 4.1.9 and do not meet exclusion criteria 4.2.3.
7. Only patients not previously referred to a Dietitian will be referred by the study team
8. Online Pain platform training and use is only required for those who met eligibility criteria 4.1.9 (First 8 participants only)
9. Online Pain platform compliance will be self-reported every 2 weeks (First 8 participants only)
10. Only completed by the participants who used the Online Pain Portal

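### The baseline muscle-mass CT is chosen by nearness alone, so it can fall after exercise has begun

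*Combined protocol and SAP*

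**What the plan says.** Section 2.4.3.1 makes muscle mass one of three exploratory measures of sarcopenia: "Changes in Muscle Mass measured at Baseline and 3-month Follow Up will also be utilized". The other two, hand grip strength and the short physical performance battery, are taken at study visits.

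The muscle-mass values come from routine abdomen CTs that the study does not schedule. The selection rule appears in four places:

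- Section 5.3: "This study will review SOC Abdomen CT scans undertaken closest to both the Baseline and 3 month follow up visit".
- Section 6.5, footnote 4: "CT scans completed closest to baseline and 3-month follow-up will be used, even if they occurred outside of the relevant visit window".
- Section 6.2.3 (baseline): "Document date of closest SOC Abdomen CT scan (ok if occurred prior to consent or greater than 14 days prior to first PREHAB session".
- Section 6.4.3 (follow-up): a scan is "ok if occurs outside of the 3 month" visit window.

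None of these gives a before-or-after limit or a maximum distance, or requires the two scans to differ. On frequency, Section 5.3 says only: "As SOC, patients will undergo Computed Tomography (CT) scans periodically throughout their pancreatic cancer diagnosis and treatment". Section 8 gives no rule for the timing or calculation of muscle-mass change.

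**The concern.** Nearness in either direction is a weak rule for a pre-treatment value. A scan three weeks after the Baseline visit is chosen over one taken five weeks before it. If session 1 has already taken place, the value labeled baseline then includes some weeks of training. Any early effect of the program is moved into the baseline and lost from the change score.

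CT is the plan's only measure of muscle mass, and Section 1.1 defines sarcopenia through loss of that mass along with muscle tone, quality and strength. The study has a single arm, so no control group is exposed to the same mistiming.

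**Working it through.** **Inputs**

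- Selection rule: nearest scan, either direction (Section 5.3; Section 6.5, footnote 4).
- Gap d from Baseline to session 1: 0 to 14 days. The Section 6.2 heading reads "Baseline Procedures (within 14 days of first PREHAB session".
- Program and follow-up length (Section 5.4): "up to 4 weeks of screening, up to 7 weeks on treatment, and 3 months of follow-up".
- Scan spacing S: not stated. Assumed 8 to 12 weeks, with 6 and 26 weeks as outer cases.
- Scan timing relative to Baseline: not stated. Assumed random, with regular scans.

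**The plan's own figure.** Section 5.4 gives about 23 weeks per subject. Screening 4 + treatment 7 + follow-up 12 to 13 = 23 to 24 weeks, which agrees. It agrees only if the three months run from the end of the program. Counted from Baseline, the total would be about 4 + 13 = 17 weeks.

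**Chance that the baseline scan falls after session 1.** With regular scans at random phase, the nearest scan lies uniformly between S/2 before and S/2 after Baseline. Hence P = max(0, (S/2 − d)/S).

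| S | d = 0 days | d = 7 days | d = 14 days |
|---|---|---|---|
| 6 weeks (42 days) | 50% | 14/42 = 33.3% | 7/42 = 16.7% |
| 8 weeks (56 days) | 50% | 21/56 = 37.5% | 14/56 = 25.0% |
| 12 weeks (84 days) | 50% | 35/84 = 41.7% | 28/84 = 33.3% |
| 26 weeks (182 days) | 50% | 84/182 = 46.2% | 77/182 = 42.3% |

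For spacing of 8 to 12 weeks and d of 7 to 14 days the range is 25% to 42%. If all 16 participants are evaluable, that is 16 × 0.25 = 4 to 16 × 0.417 = 6.7, or about 4 to 7. At 12-week spacing the chosen scan can lie as much as S/2 − d after session 1: 28 days (d = 14) to 42 days (d = 0), in a 42-day program.

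**If patients enroll soon after a scan.** If the last scan was a days before Baseline, the next comes S − a days after it and is nearer only when a > S/2. That means a last scan more than 28 days old at 8-week spacing, or more than 42 days old at 12-week spacing. If every participant's last scan is more recent than that, the share is zero. Section 6.1 does not require a recent CT at screening.

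**Chance that one scan serves both visits.** With D the time from Baseline to the 3-month visit, P = max(0, 1 − D/S). Counting follow-up from program end with 13 weeks for three months, D runs from 0 + 6 + 13 − 2 = 17 to 2 + 7 + 13 + 2 = 24 weeks. With 12 weeks for three months, the lower end is 16.

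- S of 16 weeks or less: 0.
- S = 20 weeks: 1 − 17/20 = 15% at D = 17, and 0 at D = 21 or more.
- S = 26 weeks: 1 − 17/26 = 35% at D = 17, and 1 − 24/26 = 8% at D = 24.

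**Under the fix below.** Both probabilities are zero by construction, because one scan must be on or before the first session and the other after the last.

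**The case against.** The best defense is Section 6.2.3. Documenting the closest CT is a Baseline procedure, Baseline precedes session 1, and both tolerances in its parenthesis run toward earlier dates. Section 6.4.3 is open on both sides, and the contrast suggests that a pre-exercise baseline scan was intended. As a reading of intent this is plausible. But permission to use an earlier scan does not bar a later one, and the criterion in Section 5.3 and footnote 4 is still nearness. Where the protocol wants a direction it writes one: Sections 2.4.3.4 and 2.4.3.5 count only hospitalizations and operations after Baseline.

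Scan dates must be documented, so a late baseline scan could be detected. That is true, but without a stated rule, handling it becomes a decision made after the data are in hand. Two further objections stand in full: the endpoint is exploratory in a 16-patient feasibility pilot, and the percentages rest on assumed spacing and timing.

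A reader might infer more than the documents support:

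- **One scan for both visits, forcing a change of zero.** The wording does not forbid it, but at 8- to 12-week spacing with visits 17 to 24 weeks apart its probability is zero. It needs much sparser scanning.
- **Scan-to-scan intervals of about 5 to 36 weeks.** This comes from adding two independent 6-week offsets to visits 17 to 24 weeks apart. Regular 12-week scans can differ only by multiples of 12 weeks. With visits 17 weeks apart the interval is 12 weeks (7/12 = 58%) or 24 weeks (5/12 = 42%), and with visits 24 weeks apart it is always 24.
- **An unadjusted raw difference.** Section 2.4.3.1 speaks only of changes, and no calculation is defined.
- **A compromised sarcopenia assessment as a whole.** Grip strength and the performance battery do not depend on CT timing.

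**Conclusion.** The concern holds in limited form. As written, the rule allows a scan taken after exercise has begun to serve as baseline muscle mass, and Section 6.2.3 does not close the gap. Under the assumed 8- to 12-week spacing and random timing, about 25% to 42% of participants would be affected when session 1 is 7 to 14 days after Baseline. The share falls toward zero if patients enroll soon after a scan. Duplicate use of one scan is a remote possibility that needs spacing above about 16 weeks, with follow-up counted from program end.

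The effect is confined to the exploratory CT muscle-mass component of sarcopenia. The primary feasibility endpoint and the secondary safety endpoint do not use CT. The point does not threaten the trial's main conclusion, but it is worth correcting because it biases a stated measure and costs little to remove.

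**What to change.** Align Sections 5.3, 6.2.3, 6.4.3 and footnote 4 of Section 6.5 on one rule:

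- Baseline CT: the last standard-of-care abdomen CT on or before the first PREHAB session.
- Follow-up CT: among standard-of-care abdomen CTs after the last PREHAB session, the one closest to the 3-month visit. It is then always a different scan from the baseline one.
- Reporting: give the scan-to-visit and scan-to-scan intervals alongside the change in muscle mass.
- Sensitivity: add a table limited to scans near the target visits, with the permitted distance fixed in advance. The documents give no basis for a particular distance, so the sponsor must choose it.

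This is a change of wording and needs no additional scans. The cost is that some participants may have no qualifying follow-up scan and so no muscle-mass change. Others will have an older baseline scan: at 12-week spacing the last scan before session 1 may be up to 12 weeks old, whereas the nearest scan is at most 6 weeks from Baseline. Reporting the intervals and the sensitivity table shows how much this matters.
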